9.4. Other Exploratory Efficacy Analyses

Pearson correlation coefficients will be used to assess associations between imaging endpoints, CSF biomarkers and cognitive and behavioral changes (ADAS-11, ADAS-13, ADAS-14, Cognitive Composite, Memory Composite, Executive Function Composite, Attention Composite, NTB individual items, MMSE, CDR-SB, ADCS-ADL, and ADCS-CGIC). Correlations will be calculated for baseline imaging and biomarker values and baseline efficacy measures. Additionally, correlations between change from baseline in by-visit imaging and biomarker values and change from baseline in efficacy scales will be calculated.

The composite imaging parameters that will be used for the correlations with the cognitive and functional endpoints include: the DVR composite region, the FDG composite region, the volumetric MRI composite region and the ICC composite region. Additionally, for volumetric MRI the cerebral cortex region and the lateral ventricles will also be included. For all imaging modalities the following individual parameters will also be included:

- Hippocampus

- Entorhinal cortex
- Parahippocampal cortex
- Amygdala
- Fusiform gyrus
- Lingual gyrus
- Inferior/middle temporal cortex
- Anterior cingulum
- Posterior cingulum
- Precuneus
- Prefrontal cortex
- Superior temporal cortex
- Lateral parietal cortex
- Lateral occipital cortex
- Pericentral cortex
- Medial occipital cortex

The CSF parameters that will be used for the correlations with the cognitive and functional endpoints include:

- A β 40 monomer
- A β 42 monomer
- Tau
- phospho-tau
- neurogranin
- Synaptotagmin
- synaptosomal-associated protein-25 (SNAP25)
- NFL
- YKL-40 ELISA

Additional CSF exploratory biomarkers that will be used for the correlations of the cognitive and functional endpoints include:

- neuronal pentraxin-1
- neuronal pentraxin -2
- neuronal pentraxin receptor
- complexin-2
- syntaxin-1b
- syntaxin-7
- gamma-synuclein
- rab GDI alpha
- Phosphatidylethanolamine-binding protein 1
- AP-2 complex subunit beta
- 14-3-3 protein zeta/delta

Additional exploratory plasma biomarkers and CSF biomarkers such as CSF A β oligomers and other phospho-tau species may be analyzed later when these results become available and may be included as a supplementary appendix to the CSR.

CT1812 concentrations in CSF and plasma will also be correlated with changes in biomarkers and cognitive measures.

Additional analyses and correlations may be explored as well (e.g., possibly including age, gender, education and ApoE) and will be discussed in the clinical study report (CSR).

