### **5.3 Exploratory Objective**

- To correlate changes in synaptic density, other imaging endpoints and biomarkers, with cognitive function following CT1812 treatment.
- To evaluate the plasma CT1812 metabolites in AD patients

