### ***17.2 Number of Participants Chosen for This Study***

Approximately 21 participants will be recruited to the study (7 assigned to CT1812 300 mg, 7 assigned to CT1812 100 mg, and 7 assigned to placebo).

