Pearson correlation coefficients will be used to assess associations between imaging endpoints, CSF biomarkers and cognitive and behavioral changes (ADAS-11, ADAS-13, ADAS-14, Cognitive Composite, Memory Composite, Executive Function Composite, Attention Composite, NTB individual items, MMSE, CDR-SB, ADCS-ADL, and ADCS-CGIC). Correlations will be calculated for baseline imaging and biomarker values and baseline efficacy measures. Additionally, correlations between change from baseline in by-visit imaging and biomarker values and change from baseline in efficacy scales will be calculated. Refer to the final SAP for additional details.

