4.3. Study Design

This is a single-center, Phase 1b, randomized, double-blind, placebo-controlled, parallel-group trial in adults with mild to moderate AD.

After consenting to participate in the study, screening procedures will occur between Days -60 and -1. Eligible participants will be randomized in a 1:1:1 (300 mg active: 100 mg active: placebo) ratio. The first dose of study drug will be administered in the clinic after all baseline procedures have been conducted. For the remainder of study days, participants will ingest study drug each morning at home. Participants and their study partners will return to the clinic for repeat psychometric/neurologic testing, safety studies, and PK and PD sample collection approximately every 2 weeks for the first 6 weeks and then every 3 weeks thereafter up to 24 weeks for the primary study followed by an optional double-blind extension treatment period of an additional 24 weeks (337 days +/-2) as well as a follow up visit at 2 weeks after the final treatment visit

Participants who prematurely discontinue the study for any reason will be asked to attend a final safety and efficacy visit.

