14.2.5 Imaging Outcome Summaries

- Table 14.2.5.1 Summary of Distribution Volume Ratio (DVR)
- Table 14.2.5.2 Analysis of Change from Baseline in DVR: Composite region (pooled analysis and by arm), up to 6-months
- Table 14.2.5.3 Analysis of Change from Baseline in DVR: Exploratory regions (pooled analysis and by arm), up to 6-months
- Table 14.2.5.4 Analysis of Change from Baseline in DVR: Composite region (pooled analysis and by arm), up to 12-months
- Table 14.2.5.5 Analysis of Change from Baseline in DVR: Exploratory regions (pooled analysis and by arm), up to 12-months
- Table 14.2.5.6 Summary of SUV Ratio (SUVR)
- Table 14.2.5.7 Analysis of Change from Baseline in SUVR: Composite region (pooled analysis and by arm), up to 6-months
- Table 14.2.5.8 Analysis of Change from Baseline in SUVR: Exploratory regions (pooled analysis and by arm), up to 6-months
- Table 14.2.5.9 Analysis of Change from Baseline in SUVR: Composite region (pooled analysis and by arm), up to 12-months
- Table 14.2.5.10 Analysis of Change from Baseline in SUVR: Exploratory regions (pooled analysis and by arm), up to 12-months
- Table 14.2.5.11 Summary of Volumetric MRI
- Table 14.2.5.12 Analysis of Change from Baseline in Volumetric MRI: Composite region (pooled analysis and by arm), up to 6-months
- Table 14.2.5.13 Analysis of Change from Baseline in Volumetric MRI: Exploratory regions (pooled analysis and by arm), up to 6-months
- Table 14.2.5.14 Analysis of Change from Baseline in Volumetric MRI: Composite region (pooled analysis and by arm), up to 12-months
- Table 14.2.5.15 Analysis of Change from Baseline in Volumetric MRI: Exploratory regions (pooled analysis and by arm), up to 12-months
- Table 14.2.5.16 Summary of Intrinsic Connectivity Contrast (ICC)
- Table 14.2.5.17 Analysis of Change from Baseline in ICC: Composite region (pooled analysis and by arm), up to 6-months
- Table 14.2.5.18 Analysis of Change from Baseline in ICC: Exploratory regions (pooled analysis and by arm), up to 6-months

- Table 14.2.5.19 Analysis of Change from Baseline in ICC: Composite region (pooled analysis and by arm), up to 12-months
- Table 14.2.5.20 Analysis of Change from Baseline in ICC: Exploratory regions (pooled analysis and by arm), up to 12-months
- Table 14.2.5.21 Correlation between CSF Biomarkers and Imaging endpoints at Baseline
- Table 14.2.5.22 Correlation between change from baseline in CSF Biomarkers and change from baseline in Imaging endpoints

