- Table 14.2.5.23 Correlation between Efficacy Scales and Imaging endpoints at Baseline
- Table 14.2.5.24 Correlation between change from baseline in Efficacy Scales and change from baseline in Imaging endpoints

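### SAP 9.4 does not say which arms enter the change-versus-change correlations or whether treatment is adjusted for; pooled without adjustment, a drug effect on both measures would by itself produce a correlation.

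*SAP*

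**What the plan says.** The exploratory objective in Protocol 5.3 is "To correlate changes in synaptic density, other imaging endpoints and biomarkers, with cognitive function following CT1812 treatment". For the method, Protocol 17.4 states that "Pearson correlation coefficients will be used to assess associations between imaging endpoints, CSF biomarkers and cognitive and behavioral changes" and refers to the final SAP for further detail. SAP 9.4 repeats the method and adds that "correlations between change from baseline in by-visit imaging and biomarker values and change from baseline in efficacy scales will be calculated". It lists the regions, CSF markers and scales to be used.

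Neither section says whether placebo participants are included, whether the arms are combined or kept apart, or whether treatment is a covariate. SAP 9.4 allows for further analyses, "possibly including age, gender, education and ApoE"; treatment group is not among the examples. The planned output in SAP Appendix 2 is titled "Correlation between change from baseline in Efficacy Scales and change from baseline in Imaging endpoints" and does not settle the matter.

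On the design, SAP 4.3 states that "Eligible participants will be randomized in a 1:1:1 (300 mg active: 100 mg active: placebo) ratio", and Protocol 17.2 that "Approximately 21 participants will be recruited to the study", seven per arm.

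**The concern.** These correlations are the planned link between synaptic density and cognition. A coefficient over all participants mixes two things. One is a shift between arms: the drug moved density and, separately, moved the clinical score. The other is covariation within arms: participants whose density rose more also did better. The models in SAP 9.3 and 10 already estimate the shift between arms for each measure. Only the covariation within arms adds evidence about individuals.

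The mixing is worst when the drug affects both measures, which is also when a correlation would most readily be read as support for the mechanism. Without a stated rule, the report could present such a coefficient as an individual-level link when it only restates two treatment effects.

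**Working it through.** **Inputs.** Allocation is 1:1:1 with about 21 participants, so the active fraction is p = 2/3 (14 active, 7 placebo). SAP 4.5 assumes a 30% synapse loss, recovery of a third of it on CT1812, no change on placebo, and 10% variability at each of the baseline and post-treatment scans. The documents give no effect size for any clinical scale, so those below are assumptions shown as a range.

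**Step 1: the plan's own imaging effect.** Recovering a third of 30% moves density from 0.70 to 0.80 of normal, which is 0.10/0.70 = 14.3% of baseline. If the two scan errors are independent (an assumption), the SD of the change is 10% × √2 = 14.1%. Hence d = 14.3/14.1 = 1.01. A noncentral-t calculation with 14 against 7 and one-sided alpha 0.05 gives 67.7% power. This reproduces the stated figure of about 68%, so about 1 SD is a fair reading of the planned imaging effect.

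**Step 2: the induced correlation.** Suppose the within-arm correlation is zero, the within-arm SDs are 1, and both doses have the same effect: d1 on imaging and d2 on the clinical scale. Then

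r = p(1−p)·d1·d2 / √[(1 + p(1−p)·d1²)(1 + p(1−p)·d2²)], with p(1−p) = 2/9.

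- d1 = 1, d2 = 0.5: 0.111 / √(1.222 × 1.056) = 0.10
- d1 = 1, d2 = 1: 0.222 / 1.222 = 0.18
- d1 = 1, d2 = 1.5: 0.333 / √(1.222 × 1.5) = 0.25
- d2 = 0: the numerator is zero, so r = 0

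These are magnitudes. The sign depends on which direction of the scale is worse.

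**Step 3: how often a test would reject.** The rates below come from 40,000 simulated trials per row, with 21 participants, zero within-arm correlation and a two-sided 5% Pearson test ignoring arm.

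| Imaging effect (SD) | Clinical effect (SD, assumed) | Induced r | Rejection, unadjusted |
|---|---|---|---|
| 1.01 | 0 | 0 | 5.0% |
| 0.5 | 0.5 | 0.05 | 5.6% |
| 1 | 0.5 | 0.10 | 7.0% |
| 1 | 1 | 0.18 | 12.5% |
| 1 | 1.5 | 0.25 | 19.5% |
| 1.5 | 1.5 | 0.33 | 33.4% |

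Using d = 1.01 in place of 1 changes little: 7.0%, 13.1% and 20.0% for the three clinical effects. With a graded effect on both measures (0.5 SD at the low dose, 1.01 SD at the high dose), r is 0.145 and the rate 9.9%.

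**Step 4: with adjustment.** The partial correlation given treatment group averaged about 0 and rejected in 4.9% to 5.4% of trials across the scenarios run. It has 17 degrees of freedom with three arms (21 − 4), or 18 if the active arms are combined, against 19 for the unadjusted coefficient.

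**Scale.** The two-sided 5% critical |r| is 0.43 with 21 participants and 0.75 with 7. The induced values at the planned imaging effect lie well below the first. The second shows why separate coefficients within each arm could not replace an adjusted one.

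**The case against.** A reader might infer that the SAP has chosen to pool all three arms, because the correlation tables carry no treatment label while imaging tables do, for example "Analysis of Change from Baseline in DVR: Composite region (pooled analysis and by arm), up to 6-months". The documents do not support that inference. Tables 14.2.4.2, 14.2.4.4 and 14.2.4.51 also lack a label, although SAP 9.2 and 9.3 require results by arm for their content. SAP 12.2 and Appendix 2 also say that titles may change. The plan is silent on pooling, and the objective leaves the place of placebo open.

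A reader might also infer that the plan's own assumptions imply too many false positives. They do not. SAP 4.5 assumes an effect on synaptic density only, and with that alone r is zero. All of the inflation rests on an assumed clinical effect, and Protocol 4.3 reports similar cognitive outcomes across groups in the earlier 28-day study in Alzheimer's disease. Nor does SAP 9.4 specify a test, p-value or alpha for these coefficients, so the rejection rates describe a test that might be applied, not one that is planned.

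Two further points have force. If the drug moves both measures, the marginal correlation really is non-zero and the pooled coefficient estimates it correctly; whether the marginal or the within-arm association is wanted is a choice the objective does not make. The practical stakes are also low. SAP 9.4 implies at least (4 × 16 regions + 4 composites + 2 extra MRI regions + 20 CSF markers) × 11 scales = 990 coefficients before visits and individual NTB items, with no multiplicity adjustment, so no single one would carry a decision.

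What remains is that no treatment term is named, that the two associations answer different questions, and that the reader of the report will need to know which one a coefficient shows.

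**Conclusion.** The point holds in conditional form. As written, the change-versus-change correlations leave open both the participants used and the handling of treatment. Computed over everyone without adjustment, they would show an association whenever the drug shifts both measures. At the planned imaging effect the shift in r is modest: about 0.10 to 0.25 for assumed clinical effects of 0.5 to 1.5 SD, and none if only imaging moves. These figures assume zero within-arm correlation, equal within-arm SDs, a common effect in both doses and independent scan errors.

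The shift affects the coefficient itself, so it matters for interpretation even if no p-value is reported. It does not touch the primary safety objective or the treatment comparisons, which have arm in the model. The change is nice to have, in an exploratory analysis.

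**What to change.** In SAP 9.4, state that the change-from-baseline correlations use all participants with both changes observed, and report two coefficients side by side: the unadjusted Pearson correlation, labelled as the overall association including any treatment effect, and the partial Pearson correlation adjusted for treatment group, labelled as the association within arms. State that any claim that individuals whose synaptic density rose also did better will rest on the adjusted coefficient. Apply this to Tables 14.2.4.60, 14.2.5.22 and 14.2.5.24.

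The baseline correlations stay as planned, since they precede treatment. Marking the arms on scatterplots would help but is optional.

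The cost is one additional statement in the program, one column per table, and one or two degrees of freedom. No new data are needed.

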## 2 PROTOCOL SYNOPSIS

TITLE: A Pilot Synaptic Vesicle Glycoprotein 2A (SV2A) PET Study to Evaluate the Effect of CT1812 Treatment on Synaptic Density in Participants with Mild to Moderate Alzheimer's Disease
SPONSOR: Cognition Therapeutics Inc.
PROTOCOL NUMBER: COG0105
CLINICAL STUDY PHASE: Phase Ib/2a
STUDY DRUG PRODUCT: CT1812
STUDY OBJECTIVES: Primary: To evaluate the safety and tolerability of CT1812 in AD patients  Secondary: 

To evaluate the effect of CT1812 on brain synaptic density in Alzheimer's disease (AD) patients using the SV2A PET ligand C-UCB-J

To evaluate the effect of CT1812 on cognitive and clinical outcomes in AD patients using the ADAS-Cog11 and ADAS-Cog13 (derived from ADAS-Cog14), NTB, ADCS-ADL, MMSE, CDR-SB and ADCS-CGIC

To evaluate the effect of CT1812 on brain activity in AD patients using FDG PET and resting state functional MRI

To evaluate the effect of CT1812 on brain volume in AD patients using volumetric MRI

To evaluate the effect of CT1812 on CSF pharmacodynamics in AD patients through measurement of CSF A<math>\beta</math> 40, A<math>\beta</math> 42, A<math>\beta</math> oligomers, tau, phospho-tau, neurogranin, synaptosomal-associated protein-25 (SNAP25), synaptotagmin and NFL. Additional CSF biomarkers are listed in the statistical analysis plan.

To evaluate the plasma and CSF concentrations of CT1812 in AD patients

 Exploratory: █ [REDACTED] █ [REDACTED]
STUDY DESIGN This is a single-center, Phase 1b randomized, double-blind, placebo-controlled parallel-group trial in adults with mild to moderate AD.
STUDY PROCEDURES After consenting to participate in the study, screening procedures will occur between Days -60 and -1. Eligible participants will be randomized in a 1:1:1 (300 mg active: 100 mg active: placebo) ratio. The first dose of study drug will be administered in the clinic after all baseline procedures have been conducted. For the remainder of study days, participants will ingest study drug each morning at home. Participants and their study

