CT1812 is a highly brain penetrant novel sigma-2/PGRMC1 antagonist molecule that prevents and displaces binding of A $\beta$  42 oligomers to receptors on brain cells, and clears the A $\beta$  42 oligomers into the cerebrospinal fluid (CSF). *In vitro*, in cultured rat neurons, CT1812 not only antagonizes binding of A $\beta$  42 oligomers, but also prevents A $\beta$  a oligomer-induced membrane trafficking changes. Chronic treatment with this first-in-class, highly brain-penetrant, disease-modifying oligomer receptor antagonist restores aged AD model transgenic mouse performance to normal in multiple cognitive tests. Sponsor hypothesizes that chronic treatment with CT1812

could restore neuronal plasticity compromised by A $\beta$  oligomers, and thus improve cognitive function in patients throughout the course of AD. In aged AD transgenic mice, CT1812 causes displacement of A $\beta$  oligomers into the interstitial fluid of the hippocampus and displacement of the A $\beta$  oligomers in the CSF. This approach is fundamentally different than that of other therapeutics in development (such as beta secretase cleaving enzyme [BACE] inhibitors) that focus on lowering the brain concentrations of beta amyloid protein. This product could provide the first clinical test of the hypothesis that cognitive decline in AD is related to toxic effects of A $\beta$  oligomers on synaptic function.

C-UCB-J, is a positron emission tomography (PET) tracer for quantitative synaptic vesicle glycoprotein 2A (SV2A) imaging *in vivo*. In nonhuman primates (Nabulsi et al, 2016), tracer uptake was high in gray matter, consistent with the ubiquitous expression of SV2A. Pretreatment with levetiracetam (Keppra®), an anticonvulsant that binds specifically to SV2A22-24, induced 60-90% occupancy, and self-block with unlabeled UCB-J yielded an *in vivo* dissociation constant (Kd) of 3.4 nM with a total density of receptors (Bmax) of 150-400 nM, in agreement with *in vitro* values (Gillard et al, 2006). Further, there was no evidence of specific binding in white matter. Also, in baboon, we found excellent correlation between *in vivo* PET SV2A measures and *in vitro* Western blot assays of SV2A and synaptophysin, a widely used synaptic marker, as well as with SV2A homogenate binding data (Finnema et al, 2016).

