## **4.2 Nonclinical Experience**

### **4.2.1 Nonclinical Pharmacology Studies**

CT1812 is a lipophilic isoindoline formulated as a fumarate salt, and is the result of a structure-based medicinal chemistry optimization program comprised of over 300 analogs. CT1812's properties are fully described along with all preclinical studies in the Investigator Brochure. CT1812 has a high affinity at the target receptor sigma-2/PGRMC1 (S2), and is >100-fold selective for this receptor over other receptors and ion channels. Dose-limiting toxicities at higher doses in both species appear to be hypercalcemia and renal tubular damage, both of which are non-invasively monitored via measurement of serum calcium and urinary markers of renal tubular injury such as kidney injury molecule 1 (KIM-149,50).

*In vitro* pharmacodynamic (PD) studies confirmed CT1812 target binding specificity, affinity and engagement, including the prevention and reversal of A $\beta$  oligomer binding and the prevention of A $\beta$  oligomer-induced synapse loss.

*In vivo* PD studies confirmed the desired consequences of target engagement, including cognitive improvements in an aged transgenic mouse model of AD following oral administration of an apparently tolerated dose of CT1812 daily for 9 weeks. Additional *in vivo* PD studies, using an A $\beta$  oligomer detecting microelectrode in an aged transgenic mouse model of AD, demonstrated that administration of CT1812 caused an acute increase in soluble A $\beta$  oligomers in the interstitial fluid of the hippocampus and a sustained increase in soluble A $\beta$  oligomers in the CSF of the lateral ventricle of the brain. These increases in soluble A $\beta$  oligomers occurred without a change in the amount of soluble A $\beta$  1-40, indicating that displacement of A $\beta$  oligomers occurred following treatment with CT1812.

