### **5.2 Secondary Objectives**

- To evaluate the effect of CT1812 on brain synaptic density in AD patients using the SV2A PET ligand  $^{11}\text{C}$ -UCB-J.
- To evaluate the effect of CT1812 on cognitive and clinical outcomes in AD patients using the ADAS-Cog11 and ADAS-Cog13 (derived from ADAS-Cog14), NTB, ADCS-ADL, MMSE, CDR-SB, and ADCS-CGIC
- To evaluate the effect of CT1812 on brain activity in AD patients using FDG PET and resting state functional MRI
- To evaluate the effect of CT1812 on brain volume in AD patients using volumetric MRI
- To evaluate the effect of CT1812 on CSF pharmacodynamics in AD patients through measurement of CSF A $\beta$  40, A $\beta$  42, A $\beta$  oligomers, tau, phospho-tau, neurogranin, synaptosomal-associated protein-25 (SNAP25), synaptotagmin and NFL. Additional CSF biomarkers are listed in the statistical analysis plan.
- To evaluate the plasma and CSF concentrations of CT1812 in AD patients

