#### **6.2.2 Secondary Endpoints**

The primary imaging endpoint is the change from the baseline in synaptic density as measured by differences in SV2A PET ligand C-UCB-J uptake after dosing with CT1812 versus placebo.

Cognitive and clinical outcomes:

- Mini Mental State Exam (MMSE).

- Alzheimer's Disease Assessment Scale-Cognitive Subscale (ADAS-Cog) 11 and ADAS-Cog13 (delayed recall and Number Cancellation added to ADAS-Cog11 in the ADAS-Cog13); ADAS-Cog14 includes the maze added to ADAS-Cog13.
- Neuropsychological Test Battery (NTB) including Trails A and B, Digit Span, and Letter and Category Fluency (CFT).
- Alzheimer's Disease Cooperative Study (ADCS)-Clinical Global Impression of Change (CGIC).
- ADCS-Activities of Daily Living (ADCS-ADL).
- Clinical Dementia Rating Scale – Sum of Boxes (CDR-SB)
- Composite z-score scales (Cognitive Composite score; Memory composite score; Attention composite score; Executive Function composite score).
- Imaging Outcomes
  - FDG PET
  - Functional MRI
  - Volumetric MRI
- CSF pharmacodynamics in AD patients through measurement of CSF A $\beta$  40, A $\beta$  42, A $\beta$  oligomers, tau, phospho-tau, neurogranin, SNAP25, and NFL.

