## **11 CSF COLLECTION ASSESSMENTS**

### **11.1 Lumbar Puncture**

Each participant will undergo a lumbar puncture as part of the screening process and with the Day 169 visit. Lumbar punctures will be performed by study physicians specifically trained in the

procedure. Prior to the LP, a coagulation panel will be obtained to rule out a clotting disorder. Participants will be excluded from having an LP if he or she has an allergy to all local anesthetics (such as lidocaine) and/or has any medical condition requiring treatment with warfarin or heparin. The investigator may choose to have the lumbar puncture performed with the help of fluoroscopy. Lumbar punctures performed with the help of x-rays will be done at Yale-New Haven Hospital. Obtained CSF should be sent for cell counts (white blood cells and red blood cells, with differential if either of the counts is abnormal), CSF protein, and CSF glucose.

Approximately 15 mL of CSF will be collected at each lumbar puncture.

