### **17.7 Plasma CT1812 and CSF biomarker analysis**

In addition to measuring concentrations of CT1812 in plasma and CSF, as well as CT1812 metabolites in plasma, we will also measure other CSF biomarkers associated with Alzheimer's disease (including CSF A $\beta$  40, A $\beta$  42, A $\beta$  oligomers, tau, phospho-tau, neurogranin, synaptosomal-associated protein-25 (SNAP25), synaptotagmin and NFL. Additional CSF biomarkers are listed in the statistical analysis plan.). Change from baseline in these parameters will be analyzed using the ANCOVA model described in section 17.4.

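### The SAP makes the analysis and reporting of CSF Aβ oligomers, a protocol secondary endpoint, optional, and section 11.8 does not declare the change

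*SAP*

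**What the plan says.** The secondary objective in protocol 5.2, repeated in the synopsis, lists CSF Aβ 40, Aβ 42 and then Aβ "oligomers, tau, phospho-tau, neurogranin, synaptosomal-associated protein-25 (SNAP25), synaptotagmin and NFL. Additional CSF biomarkers are listed in the statistical analysis plan". Protocol 6.2.2 lists, as secondary CSF endpoints, Aβ 40, Aβ 42 and Aβ "oligomers, tau, phospho-tau, neurogranin, SNAP25, and NFL". Protocol 17.7 names oligomers again among the CSF biomarkers and fixes the method: "Change from baseline in these parameters will be analyzed using the ANCOVA model described in section 17.4".

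In the SAP, the CSF objective (4.2) and the CSF endpoint (4.6) pass straight from Aβ 42 to tau. The pharmacodynamic list in 11.5 labels Aβ 40 and Aβ 42 as monomers and has no oligomer entry. SAP 11.7 applies the MMRM or ANCOVA of 9.3 to the CSF pharmacodynamic endpoints, once up to 6 months and once up to 12 months.

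Oligomers appear once in the SAP, in 9.4 (Other Exploratory Efficacy Analyses), which says that CSF Aβ "oligomers and other phospho-tau species may be analyzed later when these results become available and may be included as a supplementary appendix" to the clinical study report. SAP 11.8 then reports no departure from the analysis planned in the protocol.

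**The concern.** A firm commitment in the protocol (this marker, this model) becomes a double option in the SAP: the analysis need not be done and, if done, need not be reported. Anyone who follows the SAP exactly could leave a named secondary endpoint unanalysed, or decide whether to report it after seeing other results, and still comply with the plan.

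The marker is not peripheral. Protocol 4.1 describes CT1812 as displacing Aβ 42 oligomers from their receptors and clearing them into the CSF. Protocol 4.2.1 supports this with a sustained rise in soluble Aβ "oligomers in the CSF of the lateral ventricle of the brain" in aged transgenic mice. A reader of the study report would expect to see this analyte, and SAP 11.8 would tell that reader that nothing had changed.

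**Working it through.** The documents give no figure to reproduce. The check is a comparison of the lists, item by item.

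**1. Where oligomers appear**

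| Place | CSF analytes named | Aβ oligomers |
|---|---|---|
| Protocol 5.2 (same text in synopsis) | 9 | named |
| Protocol 6.2.2 | 8 | named |
| Protocol 17.7 | 9 | named, with ANCOVA |
| SAP 4.2 | 8 | absent |
| SAP 4.6 | 8 | absent |
| SAP 11.5 | 20 | absent |
| SAP 9.4 | not a list of endpoints | only mention, optional |

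The nine in protocol 17.7 are Aβ 40, Aβ 42, Aβ oligomers, tau, phospho-tau, neurogranin, SNAP25, synaptotagmin and NFL. Since the synopsis and 5.2 carry the same objective, they count as one commitment, not two.

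**2. What is lost**

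- Protocol 17.7 against SAP 11.5: 8 of the 9 are carried over, so 9 − 8 = 1 is missing (oligomers), and 20 − 8 = 12 are added.
- Protocol 6.2.2 against SAP 4.6: 7 of the 8 are kept, so 8 − 7 = 1 is missing (oligomers). Synaptotagmin brings the SAP list back to 7 + 1 = 8. It is not new, because protocol 5.2 and 17.7 already name it.

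**3. Whether SAP 11.7 still covers oligomers.** Section 11.7 analyses the CSF pharmacodynamic endpoints, and 11.5 defines these. Oligomers are not there, so no model is assigned to them. The table titles in Appendix 2 (14.2.3) speak only of CSF biomarkers in general and do not bring oligomers back in.

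**4. Whether the protocol lets the SAP remove them.** Protocol 5.2 and 17.7 say that the SAP lists additional CSF biomarkers. That allows the 12 additions. It does not provide for dropping or downgrading one that the protocol names.

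**5. Whether SAP 11.8 matches.** Moving from a definite ANCOVA in protocol 17.7 to an optional analysis in SAP 9.4 is a change, and 11.8 does not list it. SAP 1 refers to protocol Version 1.5 of 3 February 2021. The version of the protocol text reviewed here cannot be confirmed, so this step is conditional on the two agreeing.

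**6. Whether the samples are planned.** Protocol 11.1 says: "Each participant will undergo a lumbar puncture as part of the screening process and with the Day 169 visit". Change from baseline to Day 169 is therefore obtainable if the assay is run, and a single post-baseline value fits the ANCOVA. For extension participants, SAP 11.1 adds CSF at Visit 15; protocol 10.2.17 makes that puncture optional.

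**The case against.** The strongest defence is that the SAP hides nothing. Section 9.4 names oligomers and gives a timing reason: results are not yet available. The SAP describes itself as an adjunct to the protocol, so its silence does not by itself cancel protocol 17.7. The trial plans 7 participants per arm, its primary endpoint is safety, SAP 9.5 makes no multiplicity adjustment, and nothing is decided on oligomers. All of that stands, and it keeps the point modest. It does not remove it: late assay results justify a delay, but not making both the analysis and its reporting optional, nor saying that there is no change.

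Four stronger readings are tempting, but the documents do not support them.

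- *A later oligomer analysis would count as post hoc under SAP 1.* That rule concerns additional analyses explored on review of unblinded results. Oligomers are named in advance in protocol 17.7 and SAP 9.4, so the rule does not clearly reach them.
- *The SAP's statement of no changes is simply false.* It is incorrect against the protocol text reviewed, but whether it is false for Version 1.5 needs the sponsor's confirmation.
- *Results are being withheld or will be reported selectively.* Nothing suggests that. The wording leaves room for it, and no more.
- *SAP 11.8 also misstates cognitive scoring.* Imputation of scores (SAP 5.5 and 5.6 against protocol 17.9) and the ADCS-CGIC model without a baseline term (SAP 9.3 against protocol 17.4 and 17.6) are separate matters. SAP 11.8 sits within the pharmacokinetic and pharmacodynamic section, so its reach to cognitive scales is arguable. They should be handled on their own.

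**Conclusion.** The point holds. Oligomers are a protocol secondary endpoint with a stated model; the SAP drops them from every list that defines objectives, endpoints and pharmacodynamic markers, makes their analysis and reporting optional, and does not declare this.

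The size is one secondary endpoint, the only CSF analyte named in protocol 17.7 that SAP 11.5 does not carry. The harm is to complete and non-selective reporting of a marker tied to the stated mechanism. The counts describe commitments in the text; the documents allow no estimate of an effect on any result. Sample size, power, error rates, decision rules and the primary endpoint are untouched.

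The omission is certain from the two texts. The conclusion about SAP 11.8 assumes that the protocol reviewed agrees with Version 1.5 on the CSF endpoints. This should be corrected before unblinding, but it does not threaten the trial.

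**What to change.** First confirm the CSF endpoint list against protocol Version 1.5. Then take one of two routes.

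- **(a) Results will be ready by database lock.** Add Aβ oligomers to SAP 4.2, 4.6 and 11.5 and analyse them under 11.7 on the same terms as the other CSF markers: up to 6 months and, where the optional Visit 15 sample exists, up to 12 months. A Day 169 analysis alone would give oligomers less than every other marker in 11.5.
- **(b) Results will not be ready.** Before unblinding, replace the sentence in 11.8 with a declaration that this protocol secondary endpoint is deferred, and why. State that the 11.7 analysis will be run unchanged and reported in an addendum to the clinical study report whatever the result.

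Under either route, change 'may' to 'will' for oligomers in 9.4. The other phospho-tau species there can stay optional, since the protocol does not name them.

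Route (b) costs only SAP wording. Route (a) also depends on assay timing and on the CSF volume remaining, which the documents do not give. Neither needs a new visit or lumbar puncture, because CSF for pharmacodynamics is already scheduled at screening and at Visit 11.
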